### ***Determination of Sample Size***

This study is a bridging study based on an international multicenter clinical trial SADAL, and aims to verify the efficacy and safety of ATG-010 single drug in the treatment of relapsed or refractory DLBCL in the Chinese subjects. Consistent requirements of efficacy results and the SADAL study are that the point estimate of ORR in the bridging study falls within the 95% CI of the SADAL study (ORR of SADAL study: 28.3%; 95% CI: 20.7% - 37.0%). 60 subjects are

enrolled in SEARCH. If ORR reaches 28.3%, it can provide more than 90% power to make its assumed ORR to be above 20.7% and obtain sufficient safety data in Chinese subjects.

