#### Study Rationale:

ATG-010 (Selinexor) is an orally bioavailable selective inhibitor of nuclear export (SINE) compound that specifically blocks exportin 1 (XPO1). Preclinical studies showed that ATG-010 can lead to the nuclear accumulation and re-activate of tumor suppressor proteins and other growth modulators, promote rapid onset of apoptosis both *in vitro* and *in vivo* of hematological and solid tumor cells; meanwhile it has little effect on normal cells. SADAL is an international, multicenter, open IIb, ongoing study. As of 15 November 2018, the efficacy data (Karyopharm, 2018) for SADAL Study were updated and ORR was 29.6% by central radiology laboratory based on 115 subjects in modified intent-to-treat (mITT) population, including CR 9.6% and PR 20.0%; the median DOR was 9.2 months in all ATG-010 responders

(total 34 subjects; 11 CRs+23 PRs), median DOR in CR subjects was 23 months, and median DOR in PR subjects was 7.8 months. The median OS was 9.1 months in all subjects, 29.7 months for CR/PR subjects, but only 3.2 months for progressive disease/not reached (PD/NR) subjects. These results showed the correlation between tumor responses of DLBCL and clinical efficacy of treatment, the OS observed in ATG-010 non-responders with PD/NR was also consistency with published references.

Based on the encouraging clinical efficacy and safety data obtained by ATG-010 monotherapy in the treatment of subjects with recurrence or refractory DLBCL, FDA granted the rapid channel of ATG-010 monotherapy for recurrence or refractory DLBCL on 07 November 2018, aiming at accelerating the clinical study and marketing approval of ATG-010.

According to the efficacy data obtained by SADAL Study in the population of relapse or refractory DLBCL subjects in the west, the current study plans to verify the clinical efficacy of ATG-010 single drug treatment in subjects with relapse/refractory DLBCL who have received no more than 5 systematic treatment regimens in the past.

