### **Study Design**

This is an open-label, single arm, and registered study. About 60 subjects with relapsed or refractory DLBCL plan to be enrolled in about 10 study sites of the study. It is planned that at least 50% (~30 subjects) will have the GCB subtype of DLBCL. Enrolled subjects will be treated with a fixed dose, 60 mg of ATG-010, orally, twice weekly, each 4-week a cycle. Subjects should remain on the study treatment of ATG-010, until either PD or occurrence of unacceptable toxicity.

Confirmed evidence of DLBCL progressive or failed to the last treatment regimen is required for study entry, and subjects must have measurable disease at screening per the Lugano criteria for response assessment (Cheson, 2014).

Disease assessment (tumor measurement) will be made by PET-CT and Contrast-enhanced CT (Tumor measurement) at screening (within the first 14 days of Cycle 1 Day 1), enhanced CT should include the neck, chest, abdomen, pelvic cavity (including the inguinal/femoral region), if clinically indicated, as well as other anatomical sites. If CT is contraindicated, MRI scan will be performed. PET-CT and contrast-enhanced CT scans will be performed on Cycle 3 Day 1 ( $\pm$  1 week) and then every 8 $\pm$  weeks (ie, Day 1 of odd numbered cycles) until disease progression is confirmed by the central radiological review. The PET-CT is allowed at alternating assessment time points (ie, every 16 weeks, or every other scan) if PET-CT cannot be performed for every assessment. If CT scan suggests the possibility of obtaining CR, PET-CT should be performed for confirmation. Results of PET-CT and contrast-enhanced CT scans performed beyond a predetermined time point should be recorded on the eCRF and images of all disease assessment scans performed during the study period will be provided to the central radiological review.

Bone marrow aspirates and/or biopsies will be taken within 1 month prior to first dose (baseline) to assess bone marrow involvement. The bone marrow biopsy will be repeated whenever clinically indicated to confirm CR in only those subjects who had DLBCL with known bone marrow involvement prior to dosing.

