### ***Efficacy Assessment***

The primary endpoint analyses will be based on ORR data evaluated by central radiological review. The mITT population will be used for analyses of efficacy, which is defined as all subjects who received at least 1 dose of study drug administration.

Analysis of ORR will also be conducted in per-protocol population (PP) and this population will be used for supportive efficacy analysis.

The PP population will consist of the following subjects in the mITT population:

- Compliance of ATG-010 treatment  $\geq 70\%$ ;
- Subjects who have received at least one complete post-baseline tumor evaluation, except for the subjects who died before or withdrew from study;
- Subjects who have no major protocol violations that would compromise the assessment of efficacy.

Data lists of major violations that would compromise the statistical analysis will be determined prior to database lock.

The secondary efficacy endpoints include ORR evaluated by investigator, DOR and DCR evaluated by central radiological review, OS, and PFS, etc, which will be analyzed using the mITT and the per protocol populations. Time-to-event with censored value (DOR, PFS and OS, etc) will be assessed using Kaplan-Meier methods in survival analysis, 95% CIs will be provided for ORR and DCR.

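### Consistency with SADAL has two limits (ORR 20.7% to 37.0%), but the 90% power quoted for 60 subjects covers only the lower one; the rule as written is met with probability of about 84%

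*Combined protocol and SAP*

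**What the plan says.** All of this is in the synopsis, under Statistical Summaries, unless noted.

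- **Purpose.** Determination of Sample Size states: "This study is a bridging study based on an international multicenter clinical trial SADAL".
- **Rule.** The same paragraph requires that "the point estimate of ORR in the bridging study falls within the 95% CI of the SADAL study". SADAL's ORR is given there as 28.3%, with limits 20.7% and 37.0%.
- **Support for the sample size.** The paragraph ends: "If ORR reaches 28.3%, it can provide more than 90% power to make its assumed ORR to be above 20.7" percent. The upper limit of 37.0% does not enter this statement.
- **Sample size.** Study Design says: "About 60 subjects with relapsed or refractory DLBCL plan to be enrolled". Determination of Sample Size uses 60.
- **Analysis.** Efficacy Assessment says "The primary endpoint analyses will be based on ORR data evaluated by central radiological review", in the mITT population of all subjects who received at least one dose. It adds that "95% CIs will be provided for ORR and DCR". It does not repeat the consistency rule or say how an ORR above 37.0% would be read.

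**The concern.** A rule that requires an estimate to fall inside an interval can be missed on either side. The probability quoted for 60 subjects counts only misses on the low side, so it is not the probability of meeting the rule set out just before it. No probability is given for the rule itself.

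This rule is the only efficacy success rule in the text available, which is the synopsis and the schedule of assessments. Two things follow. A reader who takes the 90% as the chance of showing consistency is given too high a figure. And, read literally, the rule counts a high response rate against the bridging claim. If the upper limit were waived only after an ORR above 37.0% had been seen, that would be a post-hoc change of criterion in an open-label, single-arm trial.

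**Working it through.** **Inputs.** n = 60, true ORR p = 0.283, and limits 0.207 and 0.370, all from Determination of Sample Size. I assume that all 60 are dosed, so that the mITT denominator is 60.

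**Step 1: turn the limits into counts.** Lower: 0.207 × 60 = 12.42, so at least 13 responders are needed (12/60 = 20.0%, 13/60 = 21.7%). Upper: 0.370 × 60 = 22.2, so at most 22 are allowed (22/60 = 36.7%, 23/60 = 38.3%).

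**Step 2: reproduce the plan's figure.** With X ~ Binomial(60, 0.283):

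- P(X ≤ 12) = 0.0967
- P(X ≥ 13) = 1 − 0.0967 = 0.9033

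This reproduces the plan's figure of more than 90%. It is the chance that the point estimate clears 20.7%. It is not the power of a test that the true ORR exceeds 20.7%: an exact one-sided 0.025 test would need at least 20 responders and would have 23.2% power.

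**Step 3: apply both limits.**

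- P(X ≥ 23) = 0.0598
- P(13 ≤ X ≤ 22) = 0.9033 − 0.0598 = 0.8435

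The normal approximation agrees. The standard error is √(0.283 × 0.717 / 60) = 0.0582, which gives 0.904 for the lower limit alone and 0.837 for both limits (0.844 with continuity correction).

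**Step 4: vary the true ORR** (n = 60, limits fixed). The 28.3% row is the plan's assumption. The 29.6% row is the SADAL figure in Study Rationale ("ORR was 29.6% by central radiology laboratory based on 115 subjects"), used here only as a true rate. The other rows are values I chose.

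| True ORR | P(X ≥ 13), lower limit only | P(13 ≤ X ≤ 22), rule as written | P(X ≥ 23) |
|---|---|---|---|
| 25% | 76.8% | 75.3% | 1.5% |
| 28.3% | 90.3% | 84.4% | 6.0% |
| 29.6% | 93.5% | 84.3% | 9.2% |
| 32% | 97.2% | 79.2% | 18.0% |
| 35% | 99.1% | 65.3% | 33.8% |

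The two-limit probability peaks at 84.6%, at a true ORR of 28.9%. Beyond that, a better drug is less likely to meet the rule.

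**Step 5: vary n.** The plan gives no tolerance around 60, so I take 56 to 64 as an assumption, with p = 0.283.

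| n | Responders allowed | Lower limit only | Both limits |
|---|---|---|---|
| 56 | 12–20 | 90.5% | 81.8% |
| 57 | 12–21 | 91.7% | 85.7% |
| 58 | 13–21 | 87.5% | 80.3% |
| 59 | 13–21 | 89.0% | 80.5% |
| 60 | 13–22 | 90.3% | 84.4% |
| 61 | 13–22 | 91.5% | 84.4% |
| 62 | 13–22 | 92.6% | 84.3% |
| 63 | 14–23 | 88.9% | 83.0% |
| 64 | 14–23 | 90.2% | 83.2% |

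The two-limit figure is below 90% throughout. It first reaches 90% at n = 76 (90.04%), and stays at or above 90% for every n from 89 to 199, the largest checked.

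**Step 6: what a high-side miss looks like.** With 23 of 60 responders, the ORR is 38.3% and the exact (Clopper-Pearson) 95% interval is 26.1% to 51.8%. That interval contains SADAL's 28.3%, yet the result fails the literal rule.

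**The case against.** The strongest reply is that no printed number is wrong. The power sentence names its event and its assumed rate, and the figure is correct for that event. Guarding against the unfavourable side is ordinary practice in a single-arm efficacy trial, and the choice of 20.7% alone suggests that the sponsor regarded only a low ORR as failure. At the planning rate the whole gap is a 6.0% chance of a favourable result. The larger losses appear only at true rates above the planned one. The plan states no consequence for an ORR above 37.0%, and a fuller statistical section might qualify the rule.

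Much of this stands. The printed figure is correct, the practical effect at the planning rate is modest, and a lower-limit rule may well be what was meant. But intent is not text: the rule is written with two limits, and nothing available waives the upper one. If the intent was one-sided, the rule needs rewording; if it was two-sided, the probability does.

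A further fair point is that the lower-limit probability itself drops below 90% at 58, 59 and 63 subjects (Step 5), because responder counts are whole numbers. The 90% claim should therefore be tied to 60 treated subjects.

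**Conclusion.** The concern holds. The probability offered for 60 subjects (90.3%, correctly described as more than 90%) belongs to the lower limit alone. The consistency rule as written is met with probability 84.4%, about 6 percentage points less, and with at most 84.6% whatever the true ORR. Of the total chance of missing the rule, 0.0598 / (0.0967 + 0.0598) = 38% comes from results that are too high.

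These figures assume 60 treated subjects, limits fixed at 20.7% and 37.0%, and, for the 84.4%, a true ORR of exactly 28.3%. Between 56 and 64 subjects the two-limit probability at that ORR runs from 80.3% to 85.7%. The finding concerns the mismatch within Determination of Sample Size. It does not invalidate the design, but it should be corrected.

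**What to change.** Before data are seen, choose one of the following and repeat the chosen rule in Efficacy Assessment.

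- **(a) Both limits count.** Replace the power sentence with: *With 60 treated subjects and a true ORR of 28.3%, the probability that the observed ORR lies between 20.7% and 37.0% (13 to 22 responders) is about 84%.*
- **(b) Only a low ORR counts against bridging.** Restate the rule: *Consistency is shown if the observed ORR in the mITT population is at least 20.7%; an ORR above 37.0% is not regarded as inconsistent. With 60 treated subjects this means at least 13 responders, which has probability 90.3% if the true ORR is 28.3%.* Stating the rule as a proportion keeps it valid if the number treated is not exactly 60.

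Either option costs one or two sentences, with no added patients and no change to the estimation of ORR. Under (a) the published figure is less favourable. Under (b) an ORR above 37.0% no longer fails the rule. Raising the sample size to reach 90% under both limits would take at least 76 subjects and is not needed to remove the mismatch.

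### The 90% figure behind the 60 subjects is the chance that the observed ORR exceeds 20.7%; it is neither power to show an ORR above 20.7% nor the chance of meeting the full consistency range, which is 84%

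*Combined protocol and SAP*

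**What the plan says.** Under Determination of Sample Size, the synopsis calls the trial a bridging study and sets one efficacy requirement: that "the point estimate of ORR in the bridging study falls within the 95% CI of the SADAL study". The reference values are given as "ORR of SADAL study: 28.3%; 95% CI: 20.7% - 37.0" per cent. The justification for 60 subjects follows: "If ORR reaches 28.3" per cent, then "it can provide more than 90% power to make its assumed ORR to be above 20.7" per cent.

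Study Design gives the enrolment target: "About 60 subjects with relapsed or refractory DLBCL plan to be enrolled in about 10 study sites of the study". Under Efficacy Assessment, the mITT population is the one "which is defined as all subjects who received at least 1 dose of study drug administration", and the interval estimate is covered by the statement that "95% CIs will be provided for ORR and DCR". In the text available, which is the synopsis and the schedule of assessments, there is no null hypothesis, significance level, sidedness or confidence-limit criterion for ORR, and no role for the confidence interval in the consistency decision.

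**The concern.** Power ordinarily means the probability of rejecting a stated null hypothesis at a stated error rate. Neither is stated here, yet the sentence speaks of power for the ORR to be above 20.7%. Read alone, it suggests that a successful trial will have shown an ORR above the lower SADAL limit, with a 90% chance of doing so. A rule based on the point estimate cannot carry that inference.

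The sentence also covers only one side of the requirement set just before it. The requirement is a range with two ends; the 90% takes account of the lower end alone.

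At stake is how the primary endpoint of a single-arm study is read. This sentence is the only efficacy justification for the sample size. If 'power' is taken at face value, a result of 13 of 60 could be presented as evidence for a claim it does not support.

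**Working it through.** **Inputs.** From Determination of Sample Size: n = 60, assumed true ORR 28.3%, SADAL limits 20.7% and 37.0%. Significance levels are not given; those in step 4 are assumptions. X is the number of responders, taken as binomial(60, p).

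**1. Turn the range into counts.** 0.207 × 60 = 12.42 and 0.370 × 60 = 22.2. So 12/60 (20.0%) falls below the range, 13/60 (21.7%) is the smallest count inside it, 22/60 (36.7%) is the largest, and 23/60 (38.3%) falls above. No count lies on a limit, so it does not matter whether the limits are inclusive.

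**2. Reproduce the plan's figure.** P(X ≥ 13 | p = 0.283) = 0.903. The normal approximation agrees: (0.283 − 0.207) / √(0.283 × 0.717 / 60) = 0.076 / 0.0582 = 1.307, and Φ(1.307) = 0.904. The stated figure is therefore the probability that the point estimate exceeds 20.7%.

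**3. Apply the requirement as written, and vary the true rate.** At 28.3%, P(X ≥ 23) = 0.060, so P(13 ≤ X ≤ 22) = 0.903 − 0.060 = 0.844 (from unrounded values).

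| True ORR | P(X ≥ 13) | P(13 ≤ X ≤ 22) |
|---|---|---|
| 28.3% | 90.3% | 84.4% |
| 20.7% | 47.7% | 47.6% |
| 20% | 42.4% | 42.3% |
| 18% | 27.6% | 27.6% |
| 15% | 10.6% | 10.6% |

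**4. See whether a formal test could give 90%.** For illustration, test H0: ORR ≤ 20.7% by the exact binomial.

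| Assumed one-sided level | Responders needed | Actual size | Power at 28.3% |
|---|---|---|---|
| 2.5% | 20/60 (33.3%) | 1.5% | 23.2% |
| 5% | 19/60 (31.7%) | 3.1% | 32.6% |
| 10% | 17/60 (28.3%) | 10.0% | 54.6% |

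None of these comes near 90%, so the plan's figure cannot be the power of such a test at a conventional level.

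**5. What an observed result would support.** Exact (Clopper-Pearson) 95% intervals:

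- 13/60 (21.7%), the smallest pass: 12.1% to 34.2%.
- 17/60 (28.3%), the assumed rate: 17.5% to 41.4%, which still includes 20.7%.
- 20/60 (33.3%): lower limit 21.7%. This is the first count at which the lower limit exceeds 20.7%.

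**6. Sensitivity to the number treated.** Enrolment is approximate. With 59 treated subjects the probability of exceeding 20.7% at a true ORR of 28.3% is 89.0%, and with 58 it is 87.5%. The claim of more than 90% has almost no margin.

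**The case against.** The strongest reply is that the plan is open about its rule. It says that this is a bridging study and that consistency is judged on the point estimate; the next sentence then reads naturally as the chance that the estimate clears the lower limit. On that reading the figure is right. This stands: there is no arithmetic error, and the plan nowhere says that a pass demonstrates an ORR above 20.7% with a controlled error rate.

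It is also fair that a pass rate near one half at the threshold belongs to any point-estimate rule. A reader might take the 48% as a type I error rate that has gone wrong. The documents do not support that: they use 20.7% as the edge of a range regarded as consistent with SADAL, not as a null value, so a pass at a true rate of 20.7% is not plainly a false one. The rule also becomes stricter as the true rate falls, with 10.6% passing at 15%.

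Similarly, a reader might infer from step 4 that the trial is underpowered at 23% and needs more subjects. The documents do not support that either. Both the null value and the significance level in that calculation are assumptions brought from outside, and the plan poses no such test.

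On the upper limit, one may say that an ORR above 37.0% was never meant to count as failure. That may be so, but the requirement is written as a range and no exception is given. Lastly, a 95% CI for ORR is already planned; what is missing is the method and its place beside the consistency verdict.

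None of this removes the central point. The word power, joined to the phrase about being above 20.7%, invites an inference that the rule cannot support, and the pass rates that would correct it are not given.

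**Conclusion.** The point holds as a mislabelled and incomplete operating characteristic, not as a miscalculation. The quantity called power is a 90.3% probability that the observed ORR exceeds 20.7% when the true ORR is 28.3%. Under the same assumption the stated consistency requirement is met with probability 84.4%, about 6 percentage points less. A pass does not show that the ORR exceeds 20.7%: the range is also met 48% of the time at exactly that rate, and the smallest passing result has an exact lower limit of 12.1%.

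These figures rest on 60 treated subjects, independent binomial responses, and the upper limit being applied as written. The test-based figures of about 23% and 33% are illustrative only, because the plan states no alpha. The absence of a hypothesis or significance level is asserted only for the synopsis text available. It would be wrong to conclude that the sample size is inadequate for the bridging purpose the plan sets itself.

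**What to change.** Under Determination of Sample Size, replace the power sentence with wording such as:

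> If the true ORR is 28.3%, the probability with 60 treated subjects that the observed ORR exceeds 20.7% is 90%, and that it falls within 20.7%–37.0% is 84%. The probability of falling within the range is 48%, 28% and 11% if the true ORR is 20.7%, 18% and 15%. This describes a point-estimate consistency rule and is not power to demonstrate an ORR above 20.7%.

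If a figure for a formal test is added (about 23% at exact one-sided 2.5%, 33% at one-sided 5%), mark it as illustrative.

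Under Efficacy Assessment, state that the central-review ORR will be reported with its exact 95% CI next to the consistency verdict, and that any claim that the ORR exceeds a given value rests on the lower exact limit and not on the consistency rule.

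The change should be made before the primary analysis. It costs wording only; the sample size and the consistency rule do not change. The downside for the sponsor is that the stated figure becomes less favourable.

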### ***Efficacy Assessment***

The primary endpoint analyses will be based on ORR data evaluated by central radiological review. The mITT population will be used for analyses of efficacy, which is defined as all subjects who received at least 1 dose of study drug administration.

Analysis of ORR will also be conducted in per-protocol population (PP) and this population will be used for supportive efficacy analysis.

The PP population will consist of the following subjects in the mITT population:

- Compliance of ATG-010 treatment  $\geq 70\%$ ;
- Subjects who have received at least one complete post-baseline tumor evaluation, except for the subjects who died before or withdrew from study;
- Subjects who have no major protocol violations that would compromise the assessment of efficacy.

Data lists of major violations that would compromise the statistical analysis will be determined prior to database lock.

The secondary efficacy endpoints include ORR evaluated by investigator, DOR and DCR evaluated by central radiological review, OS, and PFS, etc, which will be analyzed using the mITT and the per protocol populations. Time-to-event with censored value (DOR, PFS and OS, etc) will be assessed using Kaplan-Meier methods in survival analysis, 95% CIs will be provided for ORR and DCR.

### ***Safety Assessment***

Data from all subjects who have received at least 1 dose of study drug administration will be used for safety analysis. Adverse events will be coded using the Medical Dictionary for Regulatory Activities (MedDRA). The severity of the adverse event will be graded according to the CTCAE, Version 4.03.

AEs will be displayed in tables and listings using MedDRA system organ class (SOC) and preferred term. subjects occurring more than one same adverse event will be counted only once when the number of subjects with adverse event was counted. Other safety endpoints including hematology and blood chemistry results will also be analyses in Safety Population.

